#### 9.4.8 TABULATION OF INDIVIDUAL PARTICIPANT DATA

Not applicable.

#### 9.4.9 EXPLORATORY ANALYSES

Multiple exploratory analyses have been planned as outlined throughout the protocol. These will be utilized to inform a definitive multicenter phase III clinical trial.

### 10 SUPPORTING DOCUMENTATION AND OPERATIONAL CONSIDERATIONS

#### 10.1 REGULATORY, ETHICAL, AND STUDY OVERSIGHT CONSIDERATIONS

##### 10.1.1 INFORMED CONSENT PROCESS

###### 10.1.1.1 CONSENT/ASSENT AND OTHER INFORMATIONAL DOCUMENTS PROVIDED TO PARTICIPANTS

Consent forms describing in detail the study intervention, study procedures, and risks are given to the participant and written documentation of informed consent is required prior to starting intervention/administering study intervention. The following consent materials are submitted with this protocol: Consent form.

###### 10.1.1.2 CONSENT PROCEDURES AND DOCUMENTATION

Informed consent is a process that is initiated prior to the individual's agreeing to participate in the study and continues throughout the individual's study participation. Consent forms will be Institutional Review Board (IRB)-approved and the participant/LAR will be asked to read and review the document. The study coordinator will explain the research study to the participant &/or LAR and answer any questions that may arise. A verbal explanation will be provided in terms suited to the participant's comprehension of the purposes, procedures, and potential risks of the study and of their rights as research participants. Participants/LAR will have the opportunity to carefully review the written consent form and ask questions prior to signing. The participants should have the opportunity to discuss the study with their family or

surrogates or think about it prior to agreeing to participate. The participant/LAR will sign the informed consent document prior to any procedures being done specifically for the study. Participants must be informed that participation is voluntary and that they may withdraw from the study at any time, without prejudice. A copy of the informed consent document will be given to the participants for their records. The informed consent process will be conducted and documented in the source document (including the date), and the form signed, before the participant undergoes any study-specific procedures. The rights and welfare of the participants will be protected by emphasizing to them that the quality of their medical care will not be adversely affected if they decline to participate in this study.

#### 10.1.2 STUDY DISCONTINUATION AND CLOSURE

This study may be temporarily suspended or prematurely terminated if there is sufficient reasonable cause. Written notification, documenting the reason for study suspension or termination, will be provided by the suspending or terminating party to study participants, investigator, funding agency, and regulatory authorities. If the study is prematurely terminated or suspended, the PI will promptly inform study participants, IRB, and sponsor and will provide the reason(s) for the termination or suspension. Study participants will be contacted, as applicable, and be informed of changes to study visit schedule.

Circumstances that may warrant termination or suspension include, but are not limited to:

- Determination of unexpected, significant, or unacceptable risk to participants
- Demonstration of efficacy that would warrant stopping
- Insufficient compliance to protocol requirements
- Data that are not sufficiently complete and/or evaluable
- Determination that the primary endpoint has been met
- Determination of futility

Study may resume once concerns about safety, protocol compliance, and data quality are addressed, and satisfy the sponsor, IRB and/or Food and Drug Administration (FDA).

#### 10.1.3 CONFIDENTIALITY AND PRIVACY

Participant confidentiality and privacy are strictly held in trust by the participating investigators, their staff, and the sponsor(s) and their interventions. This confidentiality is extended to cover testing of biological samples and genetic tests in addition to the clinical information relating to participants. Therefore, the study protocol, documentation, data, and all other information generated will be held in strict confidence. No information concerning the study or the data will be released to any unauthorized third party without prior written approval of the sponsor.

All research activities will be conducted in as private a setting as possible.

The study monitor, other authorized representatives of the sponsor, representatives of the IRB, regulatory agencies or pharmaceutical company supplying study product may inspect all documents and records required to be maintained by the investigator, including but not limited to, medical records (office, clinic, or hospital) and pharmacy records for the participants in this study. The clinical study site will permit access to such records.

The study participant's contact information will be securely stored at each clinical site for internal use during the study. At the end of the study, all records will continue to be kept in a secure location for as long a period as dictated by the reviewing IRB, Institutional policies, or sponsor requirements.

Study participant research data, which is for purposes of statistical analysis and scientific reporting, will be transmitted to and stored at the Mayo Clinic. This will not include the participant's contact or identifying information. Rather, individual participants and their research data will be identified by a unique study identification number. The study data entry and study management systems will be secured, and password protected. At the end of the study, all study databases will be de-identified and archived at the Mayo Clinic.

#### Certificate of Confidentiality

To further protect the privacy of study participants, a Certificate of Confidentiality will be issued by the National Institutes of Health (NIH). This certificate protects identifiable research information from forced disclosure. It allows the investigator and others who have access to research records to refuse to disclose identifying information on research participation in any civil, criminal, administrative, legislative, or other proceeding, whether at the federal, state, or local level. By protecting researchers and institutions from being compelled to disclose information that would identify research participants, Certificates of Confidentiality help achieve the research objectives and promote participation in studies by helping assure confidentiality and privacy to participants.

---

#### 10.1.4 FUTURE USE OF STORED SPECIMENS AND DATA

With the participant's approval and as approved by local IRBs, de-identified biological samples will be stored at the Mayo Clinic with the same goal as the sharing of data with the Mayo Clinic. These samples could be used to research the causes of anemia, its complications and other conditions for which individuals with anemia are at increased risk, and to improve treatment. The PI and study team will keep a record that will allow linking the biological specimens with the phenotypic data from each participant, maintaining the blinding of the identity of the participant.

During the conduct of the study, an individual participant can choose to withdraw consent to have biological specimens stored for future research. However, withdrawal of consent with regard to biosample storage may not be possible after the study is completed.

When the study is completed, access to study data and/or samples will be provided through the PI and Mayo Clinic.

---

#### 10.1.6 SAFETY OVERSIGHT

Safety oversight will be conducted in accordance with the Data and Safety Monitoring Plan (DSMP).

---

#### 10.1.7 CLINICAL MONITORING

Clinical site monitoring is conducted to ensure that the rights and well-being of trial participants are protected, that the reported trial data are accurate, complete, and verifiable, and that the conduct of the trial is in compliance with the

currently approved protocol/amendment(s), with International Conference on Harmonisation Good Clinical Practice (ICH GCP), and with applicable regulatory requirement(s).

It is the responsibility of the Principal Investigator to oversee the safety of the study. This safety monitoring will include careful assessment and appropriate reporting of adverse events as noted above, as well as the construction and implementation of a site data and safety-monitoring plan. Medical monitoring will include a regular assessment of the number and type of serious adverse events

#### 10.1.8 QUALITY ASSURANCE AND QUALITY CONTROL

The clinical site will perform internal quality management of study conduct, data and biological specimen collection, documentation and completion. An individualized quality management plan will be developed to describe a site's quality management.

Quality control (QC) procedures will be implemented beginning with the data entry system and data QC checks that will be run on the database will be generated. Any missing data or data anomalies will be communicated to the site(s) for clarification/resolution.

Following written Standard Operating Procedures (SOPs), the monitors will verify that the clinical trial is conducted and data are generated and biological specimens are collected, documented (recorded), and reported in compliance with the protocol, International Conference on Harmonisation Good Clinical Practice (ICH GCP), and applicable regulatory requirements (e.g., Good Laboratory Practices (GLP), Good Manufacturing Practices (GMP)).

The investigational site will provide direct access to all trial related sites, source data/documents, and reports for the purpose of monitoring and auditing by the sponsor, and inspection by local and regulatory authorities.

#### 10.1.9 DATA HANDLING AND RECORD KEEPING

##### 10.1.9.1 DATA COLLECTION AND MANAGEMENT RESPONSIBILITIES

Data collection is the responsibility of the clinical trial staff at the site under the supervision of the site investigator. The investigator is responsible for ensuring the accuracy, completeness, legibility, and timeliness of the data reported. All source documents should be completed in a neat, legible manner to ensure accurate interpretation of data. Hardcopies of the study visit worksheets will be provided for use as source document worksheets for recording data for each participant enrolled in the study. Data collected and entered into electronic case report form (eCRF) derived from source documents should be consistent with the data recorded on the source documents. Clinical data (including adverse events (AEs), concomitant medications, and expected adverse reactions data) and clinical laboratory data will be entered into REDCap electronic data capture. REDCap is HIPAA-compliant with built-in user right controls and audit trails for data security and tracking. The data system includes password protection and internal quality checks, such as automatic range checks, to identify data that appear inconsistent, incomplete, or inaccurate. Clinical data will be entered directly from the source documents.

##### 10.1.9.2 STUDY RECORDS RETENTION

Study documents should be retained for a minimum of 2 years. These documents should be retained for a longer period, however, if required by local regulations. No records will be destroyed without the written consent of the sponsor, if applicable. It is the responsibility of the sponsor to inform the investigator when these documents no longer need to be retained.

#### 10.1.10 PROTOCOL DEVIATIONS

A protocol deviation is any noncompliance with the clinical trial protocol, International Conference on Harmonisation Good Clinical Practice (ICH GCP), or Manual of Procedures (MOP) requirements. The noncompliance may be either on the part of the participant, the investigator, or the study site staff. As a result of deviations, corrective actions are to be developed by the site and implemented promptly.

These practices are consistent with ICH GCP:

- 4.5 Compliance with Protocol, sections 4.5.1, 4.5.2, and 4.5.3
- 5.1 Quality Assurance and Quality Control, section 5.1.1
- 5.20 Noncompliance, sections 5.20.1, and 5.20.2.

It is the responsibility of the site investigator to use continuous vigilance to identify and report deviations. All deviations must be addressed in study source documents, reported to the NHLBI Program Official. Protocol deviations must be sent to the reviewing Institutional Review Board (IRB) per their policies. The site investigator is responsible for knowing and adhering to the reviewing IRB requirements.

#### 10.1.11 PUBLICATION AND DATA SHARING POLICY

This study will be conducted in accordance with the following publication and data sharing policies and regulations:

National Institutes of Health (NIH) Public Access Policy, which ensures that the public has access to the published results of NIH funded research. It requires scientists to submit final peer-reviewed journal manuscripts that arise from NIH funds to the digital archive [PubMed Central](#) upon acceptance for publication.

This study will comply with the NIH Data Sharing Policy and Policy on the Dissemination of NIH-Funded Clinical Trial Information and the Clinical Trials Registration and Results Information Submission rule. As such, this trial will be registered at ClinicalTrials.gov, and results information from this trial will be submitted to ClinicalTrials.gov. In addition, every attempt will be made to publish results in peer-reviewed journals. Data from this study may be requested from other researchers within 5 years after the completion of the primary endpoint by contacting the PI.

#### 10.1.12 CONFLICT OF INTEREST POLICY

The independence of this study from any actual or perceived influence, such as by the pharmaceutical industry, is critical. Therefore, any actual conflict of interest of persons who have a role in the design, conduct, analysis, publication, or any aspect of this trial will be disclosed and managed. Furthermore, persons who have a perceived conflict of interest will be required to have such conflicts managed in a way that is appropriate to their participation in the design and conduct of this trial. The study leadership in conjunction with NHLBI has established policies and procedures for all study group members to disclose all conflicts of interest and will establish a mechanism for the management of all reported dualities of interest.

### 10.2 ADDITIONAL CONSIDERATIONS

#### Appendix 1: Visual Aid

## Anemia Study Participant

Anemia is common in ICU patients and is associated with adverse outcomes during and after hospitalization.

The goal of this clinical trial is to mitigate anemia severity and treat anemia in critically ill patients.

\_\_\_\_\_ is enrolled in the active arm of this study, which consists of:

1. *Optimized Phlebotomy*: micro blood draws, closed loop blood sampling, lab bundling
2. *Pharmacological Therapy*: IV iron +/- EPO (single dose at enrollment)
3. *Clinician Engagement & Decision Support*: visual aid, daily communications (Epic, in-person)

**What are we asking from you?** Continue to provide routine care for patients not in the active study arm (i.e. do NOT adjust practice). For patients in the active arm:

- **Remove invasive lines as soon as possible**
  - o Arterial and central venous catheters should be removed when no longer required.
  - o Do NOT draw cultures from the line that is being removed.
- **Eliminate/minimize all non-essential laboratory draws**
  - o Do NOT schedule daily labs. Assess needs daily.
  - o Avoid ABGs to assess PaO2 (SpO2 usually sufficient) or after modifying ventilator settings.
  - o Avoid ABGs to assess PaCO2 in patients with clear mentation.
  - o Avoid serial lactates in patients that are improving.
  - o Avoid frequent sodium checks for hyponatremia in absence of hypertonic saline therapy.
  - o Avoid serial coagulation tests as postoperative routine (e.g. Q6H INR, APTT, fibrinogen).
- **Consider lab holidays**
  - o No daily CBC unless concern for bleeding or new/worsening infection.
  - o No daily electrolytes unless requiring active management (e.g. large-volume diuresis).
- **Bundle labs to prevent multiple phlebotomy episodes**
  - o If new lab required, order as "add-on".
  - o If "add-on" not possible, please schedule the lab to be drawn when others will be drawn.
- **Avoid blood cultures in those with low pre-test probability of bacteremia**
  - o Isolated fever and/or leukocytosis
  - o Postop fever < 48 hours from surgery
  - o Non-severe infections (i.e. CAP, HAP, cellulitis, cystitis)
- **When blood cultures are indicated, do NOT culture all lines**
  - o Only culture from one line + one peripheral stick (2 total cultures)
- **Ensure adequate nutrition**
  - o Adequate nutrition is important for erythropoiesis
  - o Enteral tubes (NG) may cause mucosal erosion and bleeding; remove when no longer required

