### 6.3 MEASURES TO MINIMIZE BIAS: RANDOMIZATION AND BLINDING

Participants will be randomized 1:1 to active intervention vs. standard of care using a stratified permuted block design by anemia etiology (iron responsive vs. not) and ICU admission indication (surgical vs. non-surgical). Randomization will occur electronically using the REDCap randomization module. Randomization lists will be developed by the study statisticians and uploaded directly to REDCap. Study staff involved in patient care are unable to access randomization lists in advance and therefore are unlikely to predict future randomization/assignment. Clinicians and subjects will not be blinded to study interventions. However, all data analysts will be blinded to treatment allocation while the study is ongoing.

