## 8.3 ADVERSE EVENTS AND SERIOUS ADVERSE EVENTS

### 8.3.1 DEFINITION OF ADVERSE EVENTS (AE)

Adverse event means any untoward medical occurrence associated with the use of an intervention in humans, whether or not considered intervention-related (21 CFR 312.32 (a)).

As our subject population is by definition 'critically ill', it is expected that they will have many unrelated adverse health events during their hospital stay. Therefore, we will limit the scope of our adverse event monitoring and recording to focus on the following conditions:

- Study drug infusion reactions
- Venous thromboembolic disease
- Myocardial infarction
- Non-hemorrhagic stroke
- Bloodstream infections
- Hypertensive urgency or emergency in the 1 hour after study drug administration (i.e. SBP  $\geq$  200 or SBP increase by > 40 mmHg from the time of infusion start)

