#### 9.4.4 SAFETY ANALYSES

All AEs and SAEs will be presented and compared between groups. Mortality and hospital readmission rates will also be presented and compared between groups.

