## Appendix 2: Daily Rounding

## Daily rounding checklist

*Assess suitability for removal of invasive lines* (arterial line, central line)

*Review all scheduled laboratory orders*

- Does this patient *really* need labs tomorrow? Consider lab holiday
- Ensure essential labs are being drawn together (align scheduling)
- Avoid routine scheduling of labs (i.e. daily CBC, electrolytes)

*Review the necessity for additional laboratory orders*

- Does this patient *really* need blood cultures?  
Do NOT order reflexively for those with low pre-test probability of bacteremia (postop fever < 48 hours from surgery, isolated fever and/or leukocytosis, non-severe infections).  
Do NOT cultures every line. Only culture from 1 invasive line + 1 peripheral stick.
- Does this patient *really* need an ABG?  
Do I really need to trend the PaO2? Can I simply assess oxygenation with the SpO2?  
If the patient is lucid/stable, do I really care what the PaCO2 is?
- Do I need to repeat the lactate if the patient is improving?

*Discontinue unnecessary intravenous fluids*

Excessive IV fluids cause dilutional anemia (i.e. drop in hemoglobin concentration without any change in the actual red cell mass). Maintenance fluids discouraged for patients able to tolerate oral intake.

*Ensure adequate nutrition*

- Assess suitability for oral diet / dietary advancement
- Assess suitability for removal of enteral lines (NG tube)

*Ensure appropriate GI stress ulcer prophylaxis*

(MV > 48 hours, coagulopathy, recent history of GI bleeding, TBI or traumatic SC injury, severe burns; at least 2 of the following: high dose steroids, occult bleeding  $\geq$  6 days, ICU stay  $\geq$  7 days, sepsis).

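### Blood cultures are discouraged in the active arm only, so the bloodstream-infection comparison needs culture counts by arm; separately, ICU-discharge hemoglobin is modelled but not a required draw (both minor)

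*Combined protocol and SAP*

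**What the plan says.** **Blood cultures.** The visual aid in section 10.2, Appendix 1, tells staff to "Continue to provide routine care for patients not in the active study arm (i.e. do NOT adjust practice". For active-arm patients it gives three instructions on cultures: "Avoid blood cultures in those with low pre-test probability of bacteremia"; "When blood cultures are indicated, do NOT culture all lines"; and, when a catheter is taken out, "Do NOT draw cultures from the line that is being removed". The daily checklist in Appendix 2 repeats the message, including "Only culture from 1 invasive line + 1 peripheral stick". Section 6.1.1 adds twice-daily electronic messages carrying the visual-aid content. Section 6.3 states: "Clinicians and subjects will not be blinded to study interventions".

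**The safety comparison.** Section 8.3.1 restricts adverse-event recording to six conditions. "Bloodstream infections" is the only infection among them and has no case definition there. Section 9.4.4 says: "All AEs and SAEs will be presented and compared between groups". Events are sought in both arms by daily record review (8.2) and by inquiry at visits, up to 3 months after hospitalization (8.3.4). The phlebotomy outcomes in sections 3 and 4.1 are numbers and volumes of draws, not split by culture.

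**Hemoglobin.** Section 9.4.2 uses ICU discharge as a time point in the mixed model, as the cut-off for excluding withdrawals and as the value imputed for ICU deaths. It expects missingness there, other than from death, to be negligible. The Schedule of Activities (1.3) has no ICU-discharge column. Its footnote a requires hemoglobin at enrollment, hospital discharge, 1 month and 3 months; at other times it is recorded if it exists. Appendix 1 discourages a daily blood count in the active arm unless bleeding or infection is a concern.

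**The concern.** A blood culture is the main way a bloodstream infection is confirmed. If one arm is cultured less by design, the two counts are not produced by the same detection process, and record review cannot recover an infection that was never cultured.

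The event matters to this protocol. Section 2.3.3 excludes uncontrolled sepsis because of a possible infection risk with IV iron, though it adds that multiple trials in the critically ill have not shown that risk. A lower or equal active-arm count would have three explanations that look the same in the planned tables:
- true infections missed through less culturing;
- fewer contaminated cultures counted as events;
- truly fewer infections, for example through earlier line removal.

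The pilot is meant to inform a larger trial, so a reader needs to know whether culturing differed before using the infection count.

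The hemoglobin point is separate and smaller. A model time point is not a scheduled draw, and the routine tests that would usually supply it are discouraged in one arm.

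**Working it through.** **Reproducing the plan's own figure.** For 1.0 g/dL, SD 1.5 and 37 per group, power is 80.8% by the t distribution (stated 80%). 74/(1 − 0.25) = 98.7, against 100 enrolled. These agree, and nothing here changes them. With 1:1 allocation there are about 50 per arm. The documents give no infection rate, culture yield or contaminant rate, so every other infection input below is an assumption.

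**Missed infections.** Let pc be the control risk (0.05 or 0.10), the true risk ratio 1.5, f the share of infections arising while the bundle applies, and d detection in the active arm relative to control.

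Observed active risk = 1.5 × pc × (1 − f(1 − d)). Expected missed active-arm events = 50 × 1.5 × pc × f(1 − d). With independent binomials of size 50, the exact probability that the active count does not exceed the control count is:

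| pc | f | equal detection | d = 0.9 | d = 0.8 | d = 0.7 |
|---|---|---|---|---|---|
| 0.10 | 1.0 | 27.1% | 34.9% | 43.7% | 53.4% |
| 0.10 | 0.5 | 27.1% | 30.9% | 34.9% | 39.1% |
| 0.05 | 1.0 | 37.9% | 43.8% | 50.2% | 57.0% |
| 0.05 | 0.5 | 37.9% | 40.8% | 43.8% | 47.0% |

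- Mild case (f = 0.5, d = 0.9): 30.9 − 27.1 = 3.8 points and 40.8 − 37.9 = 2.9 points. Missed events are 50 × 0.15 × 0.05 = 0.375 and 50 × 0.075 × 0.05 = 0.19.
- Extreme case (f = 1, d = 0.7, pc = 0.10): 53.4 − 27.1 = 26.3 points. Missed events are 50 × 0.15 × 0.3 = 2.25.
- Milder still (f = 0.25, d = 0.9): 29.0% and 39.4%, which is 1.9 and 1.5 points above equal detection.

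**Contaminants only.** Suppose no true infection is missed and the true risk ratio is 1.0. Let contaminants counted as events be c = 0.02 or 0.04 in control, with the active arm at r = 0.7 or 0.5 of that rate. Observed risk ratio = (pc + c·r)/(pc + c). At pc = 0.05 it runs from (0.05 + 0.02)/0.09 = 0.78 to (0.05 + 0.014)/0.07 = 0.91. At pc = 0.10 it runs from 0.12/0.14 = 0.86 to 0.114/0.12 = 0.95. An apparent benefit can therefore arise with no difference in true infection.

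**ICU-discharge hemoglobin.** This was simulated with 5 × 200,000 patients per scenario under these assumptions:
- Residual SDs 1.0/1.1/1.3/1.3 at the four time points, with adjacent correlations 0.5/0.7/0.85.
- Baseline mean 8.6, SD 0.8; control mean 8.3, 8.8 or 9.3 at ICU discharge, 0.4 higher at hospital discharge, then 10.8 and 11.5.
- Treatment effects 0.2/0.4/1.0/0.8 g/dL.
- 10% ICU deaths, left out of the fit instead of being multiply imputed as planned; dropout after hospital discharge missing at random.
- Maximum likelihood, unstructured covariance, arm-by-time and baseline-by-time terms.
- Control values measured with probability 0.98. Active-arm values measured with probability 0.98 if low, otherwise 0.85, 0.70 or 0.50.

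If low is defined by baseline (below 8.2), the ICU-discharge bias is −0.001 to −0.003 g/dL. If it is defined by the unseen value itself (below 8), the bias is −0.02 to −0.05 g/dL with 11–14% of active-arm ICU survivors unmeasured, and −0.13 to −0.24 only with 34–46% unmeasured. The 1-month bias stays within 0.006 g/dL throughout (Monte Carlo standard error at most 0.004).

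**The case against.** The culture advice targets patients unlikely to be bacteremic: those with fever or a raised white count alone, fever soon after surgery, or infections that are not severe. When cultures are indicated, two are still taken. A patient who worsens leaves that group and can then be cultured, so some detection is delayed and not lost. The bundle reaches ICU teams, whereas events are collected to 3 months after hospitalization, so f = 1 is an extreme. Spill-over of the advice to control patients would narrow the gap. All of this stands and argues for the lower rows of the table.

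A case definition could sit in the Data and Safety Monitoring Plan (10.1.6) or the Manual of Procedures (10.1.10). Neither is among these documents, so one cannot say that the trial has none. Such a definition would still not supply culture counts by arm.

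The remedy is also limited. With roughly 2.5 to 7.5 expected events per arm, culture counts show that testing differed but cannot apportion a difference among its causes. Culture data sit in the medical record and could be extracted later. That is true, but committing now to how the result will be read has more value than an explanation added afterwards.

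On hemoglobin, the Schedule marks anemia labs for daily visits and section 8.1 notes that blood counts are commonly daily, so most ICU-discharge values will probably exist. What stands is the mismatch between 1.3 and 9.4.2 and the lack of a time window.

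**Conclusion.** The point holds as a minor, inexpensive improvement. The plan compares bloodstream infections between arms whose culturing is meant to differ, and it plans no measure of that difference. The size of any bias is unknown. On assumed inputs, unequal detection adds about 3–4 percentage points to the chance of seeing no excess in mild cases. The 26-point figure requires every infection to arise under the bundle and 30% of true infections never to be found. Small numbers alone account for 27–38%.

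A reader might infer that the design will conceal an infection harm from IV iron. The documents do not support that: they give no infection rate or culture yield, they report that the risk was not shown in multiple trials, and a lower count could be genuine or due to fewer contaminants. Nor is the primary result in doubt. One-month hemoglobin is a required draw and the sample size is unaffected. The ICU-discharge gap touches one secondary contrast, with near-zero bias unless a large share of active-arm values is missing for reasons tied to the unseen value.

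**What to change.** Leave the bundle unchanged.

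1. **Section 9.4.4:** report blood-culture sets per patient-day and culture positivity by arm beside the per-patient bloodstream-infection comparison. State in advance that fewer active-arm infections will not be read as evidence of safety if culturing differed. Do not make a per-culture rate the main comparison.
2. **Section 8.3.1:** apply one bloodstream-infection definition to both arms, including how probable contaminants are counted, or cite it if it exists elsewhere.
3. **Sections 1.3 and 9.4.2:** reconcile them by adding an ICU-discharge hemoglobin to the Schedule for both arms with a fixed window, accepting an existing blood count within it, and report its availability by arm.

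The cost is a few sentences, one field on the daily phlebotomy record or one record extraction, and an occasional extra low-volume draw. Items 1 and 2 disclose unequal detection; they neither remove it nor identify its cause.
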